6.4.3. Missing Data Imputation for Adverse Event and Concomitant Medication Dates

If a medication date (prior therapy or concomitant medication) or event (historical event, pre-existing condition, or AE) date is completely or partially missing, the following imputation rules should be utilized in the analysis unless otherwise stated:

- For the start date:
 - If year, month, and day are missing, then use the earlier of the patient's first visit date or the consent date.
 - If either month or month and day are missing, then use January 1.
 - If only day is missing, impute the first day of the month.
 - The imputed date should not be before the minimum of the patient's first visit or consent date.
- For the start time:
 - Impute as 23:59.
- For the end date:
 - If year, month, and day are missing, then use the patient's last visit date.
 - If either month or month and day are missing, then use December 31.
 - If only day is missing, then use the last day of the month.
 - The imputed date should not be beyond the patient's last visit date.
- For the end time:
 - Impute as 23:59.

If there is any doubt for the start and end date/times for events, the event will be flagged as treatment-emergent or follow-up emergent according to the corresponding study period. If a follow-up emergent event was already counted as treatment-emergent during the prior treatment period, it will not be counted as a follow-up emergent event. For medications, the medication will be flagged as concomitant.

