5.1.1. Screening Period (Period 1)

The duration of the Screening Period (Period 1) will be up to 28 days before randomization at (Visit 2) in the Open-Label Treatment Period (Period 2) to assess patient eligibility. The patient will sign the informed consent form (ICF) before any study assessments, examinations, or procedures are performed.

All inclusion and exclusion criteria are provided in Sections 6.1 and 6.2, respectively. Screening procedures (including complete medical history and demographics) will be performed according to the Schedule of Activities (Section 2). See Section 9.4.4.2 for details regarding required tuberculosis (TB) testing.

Investigators should review the vaccination status of their patients and follow the local guidelines for adult vaccination with nonlive vaccines intended to prevent infectious disease before therapy.

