6.9.3. Historical Illness and Pre-existing Conditions

Historical illnesses and pre-existing conditions will be classified using the latest version of the Medical Dictionary for Regulatory Activities (MedDRA) dictionary. Historical illness/condition is defined as the condition/event recorded on the *Pre-Existing Conditions and Medical History* eCRF page or on the *Prespecified Medical History* eCRF page with an end date prior to the date of informed consent. Pre-existing conditions for the Open-Label Treatment Period (Period 2) are defined as those conditions recorded on the *Pre-Existing Conditions and Medical History* eCRF page or on the *Prespecified Medical History* eCRF pages with a start date prior to the date of informed consent, and no end date (ie, the event is ongoing) or an end date after the date of informed consent. Adverse events occurring prior to the date of first study injection will also be reported for the open-label treatment period (Period 2). If a pre-existing condition worsens in severity on or after the date of informed consent, it will be considered an AE from the date of worsening onwards. Patients will only be counted once, regardless of how many conditions are included under the same System Organ Class (SOC) and Preferred Term (PT).

The number and percentage of patients with historical illnesses, pre-existing conditions and adverse events occurring prior to the first dose will be provided by treatment group, overall, and by SOC and PT for the Open-Label Treatment Period for the ITT population. For condition/event that is gender specific (as defined by MedDRA), the denominator and computation of the percentage will include only patients from the given gender.

Treatment group comparisons for ITT population will be conducted using Fisher's exact test.

Listing of historical illnesses and pre-existing conditions will be provided for ITT population.

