[12] Use of oral corticosteroids at average daily doses of >10 mg/day of prednisone or equivalent, use of variable doses within 4 weeks prior to Visit 2.	Monitor	Monitor’s list

Important Protocol Violation Category/Subcategory	Source to Identify Protocol Violation	Statistical Programming Guidance for Clinical Study Report
[13] Have received parenteral glucocorticoids within 6 weeks prior to Visit 2 or if use is anticipated during the first 24 weeks of open-label treatment period (Period 2) of the study	Monitor and Stats	Monitor’s list, or, If a patient has a reported previous therapy of parenteral glucocorticoids with and either a start or end date <42 days prior to the Visit 2 date
[14] Concomitant use of NSAIDs or cyclooxygenase - 2 inhibitors unless on a stable dose for at least 2 weeks prior to Visit 2	Monitor	Monitor’s list
[15] Use of opiate analgesics at average daily doses of >30 mg/day of morphine or equivalent or variable doses within 6 weeks prior to Visit 2	Monitor and Stats	Monitor’s list, or, If a patient has either a reported previous therapy of opiate analgesics with average dose >30 mg/day or a concomitant medication with ATC codes of N02AA with a start or end date of <42 days prior to Visit 2 date.
[16] Have received systemic nonbiologic Ps therapy other than csDMARDs or corticosteroids as indicated above (including, but not limited to oral psoralens and ultraviolet A light therapy oral retinoids, thioguanine, hydroxyurea, sirolimus, azathioprine, fumaric acid derivatives, or 1, 25 dihydroxy vitamin D3 and analogs) or phototherapy (including either oral and topical ultraviolet A, ultraviolet B, or self-treatment with tanning beds or therapeutic sunbathing) within 4 weeks prior to randomization (Visit 2); or had topical Ps treatment within the previous 2 weeks prior to randomization (Visit 2). Note WHO Group 1 weak potency topical steroids are allowed.	Monitor and Stats	Monitor’s list, or, If the patient has any record with a start date or an end date <28 days of the Visit 2 date for phototherapy for previous therapy. If the patient has any concomitant medications with a start date or an end date that is on or prior to Visit 2 date, and <28 days prior to the Visit 2 date for oral medications. If the patient has any concomitant medications with an end date that is on or prior to Visit 2 date, and ≤14 days prior to the Visit 2 date for topical medications. Note: ATC codes will be provided by medical in a separate file.

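### SAP 6.4.3 bars any imputed start date before consent even for medical history and prior therapy, so partly dated ongoing conditions fail the pre-existing definition and, if imputed dates are used, some old therapies are flagged as violations

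*SAP*

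**What the plan says.** SAP 6.4.3 opens with its scope: "If a medication date (prior therapy or concomitant medication) or event (historical event, pre-existing condition, or AE) date is completely or partially missing". For a partial start date the rules are "If either month or month and day are missing, then use January 1" and "If only day is missing, impute the first day of the month". A completely missing start date goes to the earlier of first visit and consent. Then comes the floor: "The imputed date should not be before the minimum of the patient's first visit or consent date". The rules hold unless otherwise stated, and the floor makes no distinction by record type.

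Three other places depend on these dates:

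- SAP 6.9.3 defines a pre-existing condition as one "with a start date prior to the date of informed consent, and no end date" or with an end date after consent. A historical illness is defined only by an end date before consent. The same section also reports adverse events that occur before the first injection.
- SAP Table RHCF.6.9, check [13], looks for a reported previous therapy of "parenteral glucocorticoids with and either a start or end date <42 days prior to the Visit 2 date". Check [15] (opiates) and the phototherapy and oral-medication parts of [16] also use a start or end date. Check [11] (leflunomide) and the topical part of [16] use the end date only.
- Protocol 5.1.1 says "The duration of the Screening Period (Period 1) will be up to 28 days before randomization", and has consent signed before any study procedure.

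**The concern.** A floor at consent is sensible for adverse events, and SAP 6.15.2.1 repeats it for exactly those. Medical history and prior therapy are different: they start before consent, and their dates are often incomplete. For these records the floor discards a known year or month and substitutes a date that is certainly too late.

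Two things are at stake. The first is whether the table of pre-existing conditions classifies partly dated conditions correctly. The second is whether patients appear as important protocol violators only because a start date was incomplete. SAP 6.17 uses the violation flags for a by-patient listing, a summary by treatment group, and additional analyses of the primary and/or major secondary endpoints in patients without any, or without a subset, of the violations.

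**Working it through.** The documents give no figure to reproduce on this point, so the rule is applied as written.

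**Rule.** Raw start = 1 January of the recorded year, or the first of the recorded month. Imputed start = the later of the raw start and the floor, where the floor = the earlier of first visit and consent. With consent at Visit 1, the floor is the consent date.

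**Pre-existing definition.** Take an illustrative Visit 2 of 1 June 2018 with consent and Visit 1 on 4 May 2018, 28 days before.

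- Start recorded as 2010: raw 1 January 2010, imputed 4 May 2018. Start before consent? No.
- Start recorded as March 2015: raw 1 March 2015, imputed 4 May 2018. Start before consent? No.
- Start completely missing: placed on 4 May 2018 by the rule's first bullet. Start before consent? No.
- Start recorded in full as 10 May 2010: not imputed. Start before consent? Yes.

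Without the floor, the first two pass. The imputed start also precedes the first dose, so by that date the condition is not treatment-emergent either.

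If consent came after Visit 1, which Table RHCF.6.9 lists as a violation, the floor is the Visit 1 date. The imputed start is then still before consent, and the condition stays pre-existing.

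**Start after end.** A therapy recorded as starting in 2010 and ending on 10 May 2012 receives a 2018 start, after its known end.

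**Table RHCF.6.9 checks, if they use imputed dates.** Days before Visit 2 of an imputed start, for a record dated only 2010 or March 2015:

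| Consent = Visit 1, days before Visit 2 | Imputed start, days before Visit 2 | [13], [15]: <42 | [16] phototherapy/oral: <28 |
|---|---|---|---|
| 7 | 7 | flagged | flagged |
| 14 | 14 | flagged | flagged |
| 27 | 27 | flagged | flagged |
| 28 | 28 | flagged | not flagged |

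Since 28 < 42, the date condition in [13] and [15] is met at every permitted screening length. In [16] it is met at every length shorter than 28 days. These checks accept a start or an end date, so a complete end date years earlier does not prevent the flag. Without the floor none of these records is caught on its start date: 1 March 2015 is 3 × 365 + 1 + 92 = 1,188 days before 1 June 2018.

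The notes to Table RHCF.6.9 say that a deviation coming from both sources is shown if either the monitor's list or the program finds it. Monitor review would therefore not cancel a false programmed hit.

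**The case against.** The strongest reply is that the violation flags are not established. Table RHCF.6.9 gives programming guidance, with the detail left to the ADaM specification. Neither SAP 6.17 nor the table says that the checks run on imputed dates, and the title of 6.4.3 mentions only adverse event and concomitant medication dates. This stands in part. The opening sentence of 6.4.3 plainly brings in prior therapy and medical history, so the effect on the pre-existing definition follows from the text. The effect on the violation checks is conditional.

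A reader might infer that medical-history tables simply lose partly dated conditions. The documents do not support that. Historical illness is classified by its end date, so the floor does not change its classification. A pre-existing condition moved to the consent date may reappear among the pre-dose adverse events that 6.9.3 also reports. It would be in the wrong category, but not necessarily gone.

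A reader might also infer that old prior therapies in general fall inside the washout windows. They do not: only [13], [15] and the phototherapy and oral parts of [16] use a start date. Checks [10], [12] and [14] come from the monitor's list alone.

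The SAP also protects some older dates. Onset and diagnosis of PsA and psoriasis have their own January/01 rule without a floor in 6.9.1. Prior versus concomitant status in 6.11 turns on the first-dose date, so the start floor does not normally change it. No such exception is stated for medical history or for the therapy checks.

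**Conclusion.** The floor is stated for record types that it does not fit, and it contradicts the definition in SAP 6.9.3. With consent at Visit 1, every ongoing condition with only a year or month before consent recorded fails that definition. False flags under [13], [15] and part of [16] follow only if the checks use imputed dates.

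The reach is limited. Actual eligibility does not change, since these are retrospective data checks. It would be tempting to conclude that eligible patients are removed from efficacy analyses. However, the primary and major secondary analyses use the ITT population and are unaffected. The additional analyses in 6.17 may exclude any or only a subset of violations, and that subset is not defined, so a false flag may or may not matter there. Nor do the documents give a rate of incomplete dates or of the relevant prior therapies, so no patient count can be supported.

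What remains is a real inconsistency in descriptive history tables and possibly in violation reporting. It is worth correcting because the correction is cheap.

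**What to change.** In SAP 6.4.3:

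- Limit the floor to adverse events and to medications reported as started on study.
- For historical illness, pre-existing conditions and prior therapy, impute 1 January or the first of the month without a floor, capped at any known end date.
- For these records, treat a completely missing start date as before consent. Removing the floor alone does not cover this case, because the first bullet also places it at the earlier of first visit and consent.

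In Table RHCF.6.9, state that an imputed start date alone does not trigger an eligibility violation.

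The cost is a few sentences in the SAP and a small programming change. No data collection, sample size or confirmatory analysis is affected.

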6.5. Multicenter Studies

This study will be conducted by multiple investigators at multiple sites internationally. The primary endpoint at Week 24 will be summarized by sites using descriptive statistics only.

6.6. Multiple Comparisons/Multiplicity

A multiple testing procedure for the primary and major secondary endpoints will be implemented to control the family-wise type I error rate at a 2-sided α level of 0.05. The primary and major secondary endpoints will be sequentially tested in the following order to compare ixekizumab versus adalimumab, using the primary analysis method.

1. Test 1 for Primary Endpoint – Proportion of patients simultaneously achieving ACR50 and PASI 100 at Week 24: A superiority test of the primary endpoint will be performed at an overall 2-sided $\alpha = 0.05$ using the methods described in Section 6.2.1.
2. Test 2 for Major Secondary Endpoint #1 – Proportion of patients achieving ACR50 at Week 24: If the test for the primary endpoint is significant, then a noninferiority test for the major secondary endpoint #1 will be performed using the methods described in Section 6.7.
3. Test 3 for Major Secondary Endpoint #2 – Proportion of patients achieving PASI 100 at Week 24: If the test for major secondary endpoint #1 is significant, then a superiority test for major secondary endpoint #2 will be performed using the methods described in Section 6.2.1.

If a test in this sequence is not significant, all subsequent tests will be considered nonsignificant.

There will be no adjustment for multiple comparisons for any other analyses.

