- Period 3: Post-Treatment Follow-Up Period occurring from last treatment visit during Period 2 or Early Termination Visit (ETV) up to a minimum of 12 weeks after that visit

Number of Planned Patients:

Enrolled/Randomized: 550 (275 ixekizumab; 275 adalimumab)

Statistical Analysis:

The total sample size for the study will be 550 patients randomized in a 1:1 ratio to ixekizumab or adalimumab (patients per treatment group) in Period 2.

A significance level of 0.05 is assumed for testing ixekizumab versus adalimumab.

Sample size was calculated assuming the proportion of patients simultaneously achieving ACR50 and PASI 100 as 13.6% and 31.3% in the adalimumab and ixekizumab treatment groups, respectively, as observed in the conventional synthetic disease-modifying anti-rheumatic drug (csDMARD)-experienced population from Study RHAP. According to the nQuery software, a total sample size of 550 patients (with 275 patients per treatment group) using a 2-sided Fisher's exact test at a 0.05 level of significance would yield approximately 99% power for testing ixekizumab versus adalimumab.

This sample size would yield 78% power for testing the noninferiority of ixekizumab to adalimumab at a one-sided 0.025 level of significance based on a noninferiority margin of –12% and using ACR50 response rates of 43.8% and 44.1% as observed for the ixekizumab and adalimumab treatment groups, respectively, in the csDMARD-experienced population from Study RHAP. For testing superiority of ixekizumab to adalimumab based on PASI 100 response rates of 46.9% and 23.7% as observed for ixekizumab and adalimumab in the csDMARD-experienced population from Study RHAP, this sample size would yield 99% power using a 2-sided Fisher's exact test at 0.05 level of significance.

2. Schedule of Activities

Study Schedule, Protocol I1F-MC-RHCF

	Screen-		Treat	ment Phas	se: Study I	Orug Admi	nistration	
	ing Period 1	Baseline		Ope	n-Label Tı	reatment P	eriod 2 ^a	
Visit No (V)	V1	V2	V3 ^b	V4	V5	V6	V7	V8
Study Week (W)		W0 W1 W4 W8					W16	W24
Study Days	-28d	0d	7 ± 2d	28 ± 2d	56 ± 2d	84 ± 4d	112 ± 4d	168 ± 4d
Informed consent	X							
Complete medical history	X							
Review preexisting	X							
conditions	Λ							
Age, sex	X							
Physical examination ^c	X							X
PsA classification criteria (CASPAR criteria)	X							
Inclusion/exclusion criteria	X	X						
Height		X						
Temperature		X						
Weight		X						
Sitting blood pressure and pulse	X	X ^d		X	X	X	X	X

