10.1. Sample Size Determination

Approximately 550 patients who meet all criteria for enrollment at Visits 1 and 2 will be randomized in a 1:1 ratio at Week 0 (Visit 2) in Period 2 to ixekizumab or adalimumab (275 patients per treatment group).

Sample size was calculated assuming the proportion of patients simultaneously achieving ACR50 and PASI 100 as 13.6% and 31.3% in the adalimumab and ixekizumab treatment groups, respectively, as observed in the csDMARD-experienced population from Study RHAP. According to the nQuery software, a total sample size of 550 (with 275 per treatment group) using a 2-sided Fisher's exact test at 0.05 level of significance would yield 99% power for testing ixekizumab versus adalimumab.

This sample size would yield 78% power for testing the noninferiority of ixekizumab to adalimumab at a one-sided 0.025 level of significance based on a noninferiority margin of –12% and using ACR50 response rates of 43.8% and 44.1% as observed for the ixekizumab and adalimumab treatment groups, respectively, in the csDMARD-experienced population from Study RHAP. For testing superiority of ixekizumab to adalimumab based on PASI 100 response rates of 46.9% and 23.7% as observed for ixekizumab and adalimumab in the csDMARD-experienced population from Study RHAP, this sample size would yield 99% power using a 2-sided Fisher's exact test at 0.05 level of significance.

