10.3. Statistical Analyses

10.3.1. General Statistical Considerations

Statistical analysis of this study will be the responsibility of Lilly.

Any changes to the data analysis methods related to the primary and major secondary endpoints described in the protocol, and the justification for making the change, will be documented in the SAP and/or the clinical study report (CSR). Additional exploratory analyses of the data may be conducted as deemed appropriate.

Complete details of the planned analyses will be documented in the SAP.

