10.3.1.3. Adjustment for Multiple Comparisons

A multiple testing strategy for the primary and major secondary endpoints will be implemented to control the family-wise type I error rate at a 2-sided α level of 0.05. The primary and major secondary endpoints will be sequentially tested in the following order to compare ixekizumab vs adalimumab, using the primary analysis method.

- 1. Test 1 for Primary Endpoint Proportion of patients simultaneously achieving ACR50 and PASI 100 at Week 24: A superiority test of the primary endpoint will be performed at an overall 2-sided $\alpha = 0.05$ using the methods described in Section 10.3.3.1.1.
- 2. Test 2 for Major Secondary Endpoint #1 Proportion of patients achieving ACR50 at Week 24: If the test for the primary endpoint is significant, then a noninferiority test for the major secondary endpoint #1 will be performed using the methods described in Section 10.3.3.3.
- 3. Test 3 for Major Secondary Endpoint #2 Proportion of patients achieving PASI 100 at Week 24: If the test for major secondary endpoint #1 is significant, then a superiority test for major secondary endpoint #2 will be performed using the methods described in Section 10.3.3.1.1.

If a test in this sequence is not significant, all subsequent tests will be considered nonsignificant.

There will be no adjustment for multiple comparisons for any other analyses.

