5.2. Determination of Sample Size

Approximately 550 patients who meet all criteria for enrollment at Visits 1 and 2 will be randomized in a 1:1 ratio at Week 0 (Visit 2) in Period 2 to ixekizumab or adalimumab (275 patients per treatment group).

Sample size was calculated assuming the proportion of patients simultaneously achieving 50% improvement in American College of Rheumatology criteria (ACR50) and 100% improvement from baseline in Psoriasis Area and Severity Index criteria (PASI 100) as 13.6% and 31.3% in the adalimumab and ixekizumab treatment groups, respectively, as observed in the conventional synthetic disease-modifying anti-rheumatic drugs (csDMARD)-experienced population from Study I1F-MC-RHAP (RHAP). According to the nQuery software, a total sample size of 550 (ie, 275 per treatment group) using a 2-sided Fisher's exact test at 0.05 level of significance would yield approximately 99% power for testing ixekizumab versus adalimumab.

This sample size would yield 78% power for testing the noninferiority of ixekizumab to adalimumab at a 1-sided 0.025 level of significance based on a noninferiority margin of -12% and using ACR50 response rates of 43.8% and 44.1% as observed for the ixekizumab and adalimumab treatment groups, respectively, in the csDMARD-experienced population from Study RHAP. For testing superiority of ixekizumab to adalimumab based on PASI 100 response rates of 46.9% and 23.7% as observed for ixekizumab and adalimumab in the csDMARD-experienced population from Study RHAP, this sample size would yield approximately 99% power using a 2-sided Fisher's exact test at 0.05 level of significance.

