6.12.1.2. Methodology for Major Secondary Outcomes

The major secondary endpoints are as follows:

1. Proportion of patients achieving ACR50 in each treatment group at Week 24
2. Proportion of patients achieving PASI 100 in each treatment group at Week 24

The analyses of the secondary endpoints will be based on the ITT population in the Open-Label Treatment Period (Period 2) comparing ixekizumab versus adalimumab at Week 24 using methods described in Section [6.7](#) for the major secondary endpoint #1 and using methods from Section [6.2.1](#) for the major secondary endpoint #2. Missing data will be imputed using the NRI method described in Section [6.4.1](#).

A multiple testing procedure, as described in Section [6.6](#), will be used for testing the primary and major secondary endpoints.

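### Does the 99% power quoted for PASI 100 superiority overstate what the fixed testing sequence can deliver?

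*SAP*

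**What the plan says.** Three places give the planning powers: the Statistical Analysis part of the Protocol Synopsis, Protocol 10.1 and SAP 5.2. Each lists about 99% for the composite primary endpoint, then the noninferiority figure, then PASI 100. On noninferiority, Protocol 10.1 reads "This sample size would yield 78% power for testing the noninferiority of ixekizumab to adalimumab at a one-sided 0.025 level of significance". The PASI 100 figure comes in the next sentence of the same paragraph: "this sample size would yield 99% power using a 2-sided" Fisher test in the Synopsis and Protocol 10.1, and "this sample size would yield approximately 99% power using a 2-sided" Fisher test in SAP 5.2.

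The testing order is set elsewhere, in Protocol 10.3.1.3 and SAP 6.6. Its purpose is "to control the family-wise type I error rate at a 2-sided α level of 0.05". The order is composite superiority, ACR50 noninferiority, PASI 100 superiority. On the last step SAP 6.6 says "If the test for major secondary endpoint #1 is significant, then a superiority test for major secondary endpoint #2 will be performed", and Protocol 10.3.1.3 adds the stopping rule: "If a test in this sequence is not significant, all subsequent tests will be considered nonsignificant". SAP 6.12.1.2 confirms that this procedure "will be used for testing the primary and major secondary endpoints".

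No section gives the power of PASI 100 within the sequence, or a reason for placing ACR50 noninferiority ahead of it. The order does match the order in which the objectives are listed in the Synopsis, in Table RHCF.4.1 of both documents and in SAP 6.12.1.2.

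**The concern.** Read alone, the sample-size text suggests about a 1% risk of missing the PASI 100 claim. Under the planned procedure, PASI 100 is never formally tested if ACR50 noninferiority fails, and the plan itself allows a 22% chance of that failure (100% − 78%). The least powerful of the three tests therefore controls access to a nearly certain one. It is also a test for which the plan assumes almost no true difference (43.8% against 44.1%), so modest departures from the planning rates change its power noticeably.

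At stake would be the formal claim on one of only two major secondary objectives. The PASI 100 estimates would still be reported, and PASI 100 is half of the primary endpoint.

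**Working it through.** **Inputs** (SAP 5.2 and 6.7; the same values are in Protocol 10.1 and 10.3.3.3): 275 per arm. Rates for ixekizumab and adalimumab: composite 31.3% and 13.6%; ACR50 43.8% and 44.1%; PASI 100 46.9% and 23.7%. Noninferiority margin −12%, judged by the lower limit of a two-sided 95% Wald interval without continuity correction. Nonresponder imputation on the ITT population keeps all 275 per arm in the denominator.

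**Step 1: the stated powers, each test alone.**
- Composite, exact two-sided Fisher power: 99.87% (stated: about 99%).
- PASI 100, exact two-sided Fisher power: 99.99% (stated: 99%).
- ACR50 noninferiority: SE = √(0.438×0.562/275 + 0.441×0.559/275) = 0.0423. Power = Φ((0.12 − 0.003)/0.0423 − 1.96) = 78.9%. Exact enumeration of the interval rule in SAP 6.7 gives 79.7%; a continuity correction, which the SAP does not use, would give 76.4% (stated: 78%).

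All three stated figures reproduce to within 2 points, so there is no arithmetic error.

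**Step 2: bounds in sequence from the stated powers alone.** A PASI 100 claim needs all three tests to succeed.
- Upper bound: min(0.99, 0.78, 0.99) = 78%.
- Lower bound: 0.99 + 0.78 + 0.99 − 2 = 76%.

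Neither bound needs an assumption about correlation between endpoints.

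**Step 3: direct calculation.** The marginal and simultaneous rates fix the joint distribution in each arm:

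| | Both | ACR50 only | PASI 100 only | Neither |
|---|---|---|---|---|
| Ixekizumab | 31.3% | 12.5% | 15.6% | 40.6% |
| Adalimumab | 13.6% | 30.5% | 10.1% | 45.8% |

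One million simulated trials, with pooled z-tests for superiority and the SAP 6.7 interval for noninferiority, give:
- composite alone: 99.9%
- ACR50 noninferiority alone: 79.7%
- PASI 100 alone: 99.99%
- all three in sequence: 79.7%

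Fisher tests for the two superiority steps give 79.6%. The confirmatory superiority analysis in SAP 6.2.1 is logistic regression, which was not simulated. Since both superiority tests succeed almost always, the choice among these methods should matter little.

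So the in-sequence figure is the noninferiority power under another name. Essentially all of the shortfall from 99% (100% − 79.7% = 20.3%) comes from that one step.

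**Step 4: what reordering would do.** With PASI 100 second and ACR50 noninferiority third, at the planning rates PASI 100 would be claimed in 99.9% of trials and ACR50 noninferiority still in 79.6%. If the PASI 100 effect is smaller than planned, ACR50 noninferiority loses power (ixekizumab PASI 100 and composite rates below are assumed, except that 31.3% is the planning value):

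| Ixekizumab PASI 100 | Ixekizumab composite | Order as written | Swapped | Loss, points |
|---|---|---|---|---|
| 37% | 24.7% | 75.2% | 71.8% | 3.4 |
| 37% | 31.3% | 79.7% | 74.9% | 4.8 |
| 35% | 23.4% | 70.0% | 62.8% | 7.2 |
| 35% | 31.3% | 79.7% | 68.1% | 11.6 |

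**The case for a change.** The best case for a change is that disclosure is cheap and the difference, about 20 points, is not trivial. The Synopsis does not describe the sequence, so someone who reads only the Synopsis cannot work out the cap. In the full documents a reader must put SAP 5.2 together with 6.6, or Protocol 10.1 with 10.3.1.3. The figure is also sensitive: with the other rates fixed, the chance of a PASI 100 claim is 56.8% if ixekizumab ACR50 is 41%, 74.0% at 43% and 86.7% at 45% (assumed values). Protocol 3.2 reports 40.2% for the Q4W regimen in Study RHAP.

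Most of the facts in this stand, but they do not show a defect. The power statements name a test, a level and a sample size, and the design delivers what they say. None of them offers 99% as the probability of a claim after gating. The missing number follows in one step from two printed facts. The sensitivity belongs to the noninferiority test itself, whose power the plan already gives as 78%. The 40.2% comes from the whole RHAP population, whereas planning used its csDMARD-experienced part, and the same section gives 46.6% for Q2W, on the other side of the assumed 43.8%.

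The order can be questioned, but it is a choice. ACR50 noninferiority is the first-listed major secondary objective, and Protocol 3.1 asks whether biologics with different mechanisms have comparable efficacy. The order as written withholds a formal skin claim unless joint response has been shown to be noninferior. The swap would permit that claim when joint noninferiority fails, and would cost noninferiority several points if the skin effect is smaller than planned. It would also be a substantive change of hierarchy in an open-label trial: Protocol 10.3.1 requires that "Any changes to the data analysis methods related to the primary and major secondary endpoints described in the protocol" be documented with a justification, and it would have to be made without sight of comparative data.

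**Conclusion.** No change is needed. The 99% is a correct per-test figure. The chance of a confirmatory PASI 100 claim under the sequence is at most the stated 78%, or about 79.7% by direct calculation with the SAP 6.7 interval rule. The bounds of 76% to 78% rest only on the stated powers; the 79.7% rests on the planning rates and 275 patients per arm.

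The sequence controls the family-wise error rate, and the gate can only withhold a claim; it cannot create a false one. A sentence spelling out the cap would be harmless if SAP 5.2 were being revised for another reason, but no test, estimate or conclusion depends on it. Moving PASI 100 up the order trades one objective against another, and the plan's existing order is a defensible choice.
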